10.4 Criteria for Discontinuation

Safety will be monitored by the dedicated SMC, led by a qualified HIV specialist in the University of Utah Department of Medicine (see Section 13 below). The SMC will have full and final authority to stop the study at any point for safety concerns. Given the unknown safety profile of *Euphorbia kansui*, the first participant in each dosing level will complete 5 days of study prior to any further participants commencing the study. The decision to proceed with further drug administration will be taken by the Principal Investigator, taking into consideration clinical and laboratory adverse events. The decision to proceed with the next dosing level will be taken by the SMC. Specifically, dosing will be paused and the SMC will be consulted if one Grade 4 or two Grade 3 drug related adverse events or laboratory abnormalities are reported.

In addition, since there is currently insufficient data demonstrating the effect of kansui on antiretroviral therapy or other concomitant medications (and vice versa), we will evaluate serum HIV-1 RNA levels using standard clinical assays within each dosing cohort prior to dose escalation. HIV RNA measures will be collected on the initial dosing day(s) (Day 1 for Cohort 1, Days 1-3 and 102-104 for Cohort 2), at the 24-hour post dosing follow-up visits on Day 2 (for Cohort 1) and Days 4 and 105 (for Cohort 2), and on Day 31 and 132. This is to safeguard against the potential risk of virologic failure and/or the development of resistance due to sub-therapeutic antiretroviral therapy drug levels in study participants.

Specifically, safety discontinuation criteria will include:

1. Any serious adverse event assessed as at least possibly related to study treatment:
 - a. Any Grade 4 drug-related adverse event or laboratory abnormality
 - b. Two Grade 3 drug-related adverse event or laboratory abnormality
2. Virologic failure (defined as any two consecutive HIV-1 RNA levels >200 copies/mL or a single HIV-1 RNA level >1000 copies/mL). These values would be above the levels predicted to be seen with HIV reactivation with most current latent reactivating agents and are safety stopping criteria currently used for other HIV latent reactivating agent trials, e.g., the AIDS Clinical Trials Group (ACTG 5336) trial, evaluating the role of Sirolimus on immune activation and the latent reservoir in chronic HIV-infected, ART-suppressed individuals.
3. Pregnancy or breastfeeding
4. Requirement for prohibited concomitant medications (see section 7.1)
5. Clinical reasons believed life threatening by the physician, even if not addressed in the toxicity section of the protocol

The specific adverse events that will be solicited include: diarrhea, gastrointestinal irritability, gastrointestinal bleeding, headache, and symptoms of dehydration (light-

headedness, tachycardia). For the most likely expected reported adverse event, diarrhea, we will strictly adhere to established toxicity grading used by the National Cancer Institute for chemotherapy-induced diarrhea.^{39,40}

Grade	Description
1	Increase of fewer than four stools per day over baseline
2	Increase of four to six stools per day over baseline
3	Increase of seven or more stools per day over baseline; incontinence; hospitalization indicated
4	Life-threatening consequences; urgent intervention indicated
5	Death

** Based on information from National Cancer Institute, 2010.*

If stopping/pausing criteria are not met, the remainder of the dosing cohort will be enrolled/dosed the subsequent week. The study will proceed to the next dosing level provided the stopping/pausing criteria are not met. A University of Utah Department of Medicine faculty member who is not otherwise involved in the study and who will not communicate with the study investigators regarding any aspect of the SMC reports will prepare the monitoring reports. The SMC will review accrual, adverse events summaries, CD4+ T-cell counts and HIV RNA levels/suppression over time, off-study rates and completeness of follow-up, by dose cohort.

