Subjects will initiate dosing on separate days. All safety data from each cohort (through week two of observation) will be collated and presented to an SMC before we escalate to the next dose level, as described below. We hypothesize that 1 g of kansui powdered, measured and prepared as tea, given as a single or 3 consecutive daily doses will be safe and well tolerated. We also hypothesize that kansui given as a single or 3 consecutive daily doses may induce T cell activation (CD69, CD38, and/or HLA-DR expression on CD4+ and CD8+ T cells) and latent HIV reactivation (cell-associated HIV RNA and plasma HIV RNA).

Participants will be screened for eligibility. Individuals meeting inclusion criteria without meeting exclusion criteria will be enrolled in the study in sequential dosing cohorts as below. The following treatment regimens will be used:

- Cohort 1: Kansui Phase of (1 g) x 1 dose (the first N = 2 participants)
- Cohort 2: Kansui Phase of (1 g) x 3 consecutive daily doses that is either preceded or followed by a Placebo Phase (the final N = 6 participants)

Study participants will be followed for 31 days following each treatment phase. There will also be a 56-day washout period in between the two treatment phases. The total duration of the study is expected to be up to 45 days for Cohort 1 and up to 146 days for Cohort 2 (See Study Events Table).

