8 STUDY TREATMENTS

8.1 Method of Assigning Participants to Treatment Groups

Cohort 1: NA

Cohort 2: Participants will be randomized to either kansui versus placebo treatment first using a random number generator. Whichever treatment the participant receives first, they will receive the other treatment (placebo or kansui) for their second treatment starting at Day 102 (See Study Events Table in Section 9 below).

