8.2 Blinding

Cohort 1: NA

Cohort 2: The order in which participants in Cohort 2 complete the two treatment phases (i.e., kansui and placebo) will be unknown to both the participants and the PI/study team. Both the kansui and placebo will be prepared and delivered to the Center for Clinical & Translational Science (CCTS) in identical, HDPE vials (described later in section 8.3.3). Upon arrival at the CCTS, the HDPE vial will be received by a CCTS study nurse. At the appropriate time, the CCTS study nurse will prepare the tea (either kansui or placebo) in the med room of the CCTS, out of sight of the study participant, study coordinator, and study site PI to maintain double blinding. Following preparation the study nurse will administer the tea (kansui/placebo) to the participant following protocol section 8.4.3. The University of Utah Investigational Drug Services (“UU IDS”) will randomize each participant in Cohort 2 according to the methods described in Protocol section 8.1. In the event that participant experiences an adverse event that requires the identity of the study drug be revealed, the PI will be able to contact UU IDS to break the blind. In the event that a participant blind is broken, the study PIs will determine the impact upon the unblinded subject’s continued participation in the study and if a replacement subject is needed on a case-by-case basis.

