13 DATA SAFETY MONITORING

The study will require 48-hour reporting by sites of all laboratory values, signs/symptoms, and SAEs. The study will have intensive Phase I safety monitoring, which will include regular and frequent team review (every week for the first 2 months of the study; then every two weeks thereafter) of all reported events. In addition, for any Grade 3 or 4 events, sites will be instructed to contact the study team by email.

Safety monitoring will include team review of adverse events (including all reported signs/symptoms, laboratory abnormalities, diagnoses, and SAEs) and team assessment as to the possible relationship of adverse events to the study treatment. The review will also include assessment any participants with an unconfirmed CD4+ T cell or HIV RNA measurement indicating a potential safety endpoint. Regular team monitoring will also assess early study discontinuations and visit/sample completeness. In addition, study accrual and baseline characteristics of study participants will be reviewed periodically during accrual. After a dose cohort has completed accrual and sufficient follow-up time is available, the team will evaluate whether to dose-escalate and open the next dose cohort to accrual, as described below.

Safety Monitoring Committee (SMC). We have established an independent Safety Monitoring Committee (SMC) for this study. As safety concerns for kansui pertain primarily to gastrointestinal symptoms (expected to be mild) and perhaps control of HIV infection, these areas are represented on the SMC by well-recognized experts: [name] (Professor of Medicine, University of Utah, expert in epidemiology, infectious disease, HIV, and clinical research), [name] (Assistant Professor of Medicine, UCSF, expert in clinical gastroenterology), [name] (Professor of Medicine, UCSF, and an expert in complementary medicine) and [name] (Associate Professor of Medicine, UCSF, and expert on HIV management and clinical trials).

The committee will be co-chaired by [name] at the University of Utah and [name] at UCSF, who both have experience in the regulatory aspects of clinical trials and will independently deliberate using study data.

The SMC will meet after completion of each dose cohort to review safety data. The meeting will occur no earlier than two weeks after the last dose. The decision to move to the next dose cohort will be made by the SMC, after consultation with the study investigators.

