A study data coordinator will produce administrative reports regularly describing study progress including the following: (1) accrual, (2) demographics, (3) study subject status, (4) laboratory data, and (5) number and type of serious AEs. Reviews will be communicated to the University of Utah and UCSF Committee on Human Research (CHR), study sponsor, and/or federal agencies, as appropriate. The SMC will have access to treatment assignment. The study will be discontinued if the SMC determines that it is in the best interest of the subjects.

Grade 1 or 2 AEs will not result in any change to the study plans. If there is evidence for a Grade 3 AE that is not caused by the study drug, the study will continue as planned. On

the other hand, Grade 3 AEs thought to be possibly caused by the intervention and any Grade 4 AEs will result in a hold on any future enrollments until a decision to proceed or to stop the study is made by the SMC

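### In Cohort 2 the 5-day sentinel step can be passed by a participant on placebo; separately, the synopsis misstates the virologic stopping threshold

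*Combined protocol and SAP*

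**What the plan says.** **Sentinel step.** Section 10.4, and the synopsis under Planned Interim Analyses, give kansui's unknown safety as the reason for this rule: "the first participant in each dosing level will complete 5 days of study prior to any further participants commencing the study". The five days are not tied to a kansui dose.

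For Cohort 2, Section 8.1 states: "Participants will be randomized to either kansui versus placebo treatment first using a random number generator". The first participant is not exempted, and anyone given placebo first receives kansui only from Day 102. Under Section 8.2 the order "will be unknown to both the participants and the PI/study team".

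On release of the others, Section 10.4 says: "The decision to proceed with further drug administration will be taken by the Principal Investigator". If no stopping or pausing criterion is met, "the remainder of the dosing cohort will be enrolled/dosed the subsequent week". The Safety Monitoring Committee (SMC) has access to assignments, but Section 13 sets its scheduled review later: "The SMC will meet after completion of each dose cohort to review safety data".

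**Virologic stopping rule.** The synopsis counts any HIV-1 RNA value above 200 copies/mL as virologic failure, or a single value above 1000. Sections 2.1 and 10.4 require two consecutive values above 200, or a single value above 1000.

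**The concern.** A sentinel step should give information on the new regimen before more people are exposed to it. In Cohort 2 the new element is three daily doses instead of one. If the first participant is in the placebo phase, the step is satisfied and yields nothing about that element. The person opening the gate cannot tell, because of the blind, and no one who holds the allocation (pharmacy or SMC) is asked to check. Several first-ever three-day courses could then begin close together, since Section 4.1 says only "Subjects will initiate dosing on separate days" and sets no minimum interval.

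The gap is confined to Cohort 2. Cohort 1 is open-label kansui, so its sentinel necessarily receives the product.

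The virologic point is smaller. The synopsis wording makes its own 1000-copy limb redundant and leaves two stopping rules in one protocol.

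**Working it through.** The protocol gives no figure for this step, so there is none to reproduce. The check takes the timeline, the chance of a placebo sentinel, and what the step can then show.

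**1. Timeline.** Follow-up ends on Day 31 and washout lasts 56 days: 31 + 56 = 87. Rescreening is on Day 88, and 88 + 14 = 102. A placebo-first sentinel thus takes no kansui until Day 102, while the others may start the week after the five days end.

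**2. Chance that the sentinel is on placebo.** This is 1 minus the share allocated to kansui first. The ratio and any blocking are not stated, so these shares are assumptions.

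| Kansui-first : placebo-first | Chance of placebo sentinel |
|---|---|
| 2:1 | 1 − 2/3 = 33% |
| 1:1 | 1 − 1/2 = 50% |
| 1:2 | 1 − 1/3 = 67% |

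**3. Who follows a placebo sentinel.** Five participants remain.
- Simple 1:1 randomisation: at least one is kansui-first with probability 1 − 0.5⁵ = 0.969, and at least two with probability 1 − 0.5⁵ − 5 × 0.5⁵ = 0.813.
- Balanced 3:3: exactly three of the five are kansui-first.
- Overall chance of a placebo sentinel followed by at least one kansui-first participant: 0.5 × 0.969 = 0.484 (simple) or 0.50 (balanced).

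**4. What the step can show.** Let p be the fraction of participants who, within five days of starting three-dose kansui, have a toxicity that would bear on the decision to proceed. The documents give no value, so p is assumed. As written, the chance that the step shows it is p × (kansui-first share). With a guaranteed kansui sentinel it is p. The gain is p × (chance of placebo sentinel).

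| p (assumed) | As written, 1:1 | Kansui sentinel guaranteed | Gain at 1:1 | Gain, 2:1 to 1:2 |
|---|---|---|---|---|
| 10% | 5% | 10% | 5 points | 3 to 7 points |
| 20% | 10% | 20% | 10 points | 7 to 13 points |
| 50% | 25% | 50% | 25 points | 17 to 33 points |

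One sentinel is weak against uncommon toxicity in either case.

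**5. Virologic rule.** The definitions differ on one pattern only: an unconfirmed single value of 201 to 1000 copies/mL. The synopsis stops dosing; Sections 2.1 and 10.4 do not. Any value above 1000 also exceeds 200, so the synopsis's second limb never operates by itself.

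**The case against.** The strongest reply is that the gap is narrow and well buffered.

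- Two Cohort 1 participants take the same 1 g dose open-label, and the SMC reviews those data before escalation.
- Three macaques had three-day dosing without adverse clinical events (1.1.b). A cumulative 3 g lies within the 1 to 8 g single-dose range that Section 1.2 calls well tolerated, and below the 9 to 15 g linked to serious effects in Section 2.1.
- Section 13 stops enrolment after an event: "Grade 3 AEs thought to be possibly caused by the intervention and any Grade 4 AEs will result in a hold". There is also 48-hour reporting, weekly team review in the first two months, code-breaking for an adverse event, and SMC authority to stop at any time.
- The phrase about each dosing level could be read as meaning kansui dosing. The investigator might also guess allocation from bowel effects, since Section 2 reports elimination within two hours of 1 g.

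Much of this stands as a limit on severity. It does not close the gap. The human and SMC evidence before Cohort 2 covers a single dose, and the animal evidence is three animals. Holds and code-breaking act after an event, whereas a sentinel is meant to inform beforehand. The kansui reading has no step that applies it, and a blinded investigator cannot apply it; the gate does not ask for a guess.

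It is also fair that p is assumed and that its meaning depends on which stopping rule is in view. The 50% row would be hard to support for Grade 3 or 4 events, because Section 13 expects gastrointestinal symptoms to be mild. The table shows what the rule loses proportionally; it does not forecast harm.

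**Conclusion.** The concern holds. Followed as written, the Cohort 2 sentinel step can release the remaining participants with no information on the three-dose regimen. At an assumed 1:1 allocation this happens half the time (33% to 67% for 2:1 to 1:2), and the step's chance of showing any given toxicity is halved. The exposure concerns repeat dosing only and other safeguards limit it, so this should be fixed as an inexpensive improvement; it does not show that safety oversight has failed.

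The synopsis definition of virologic failure is wrong as written and conflicts with Sections 2.1 and 10.4. It errs on the cautious side, and Section 13 already has the team review unconfirmed HIV RNA values, so the harm is operational. No estimate is made of how many results would fall between 201 and 1000 copies/mL.

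**What to change.** **Sentinel step.** In Section 10.4 and the synopsis, require at least one participant to have completed five days in a kansui phase before the remainder of Cohort 2 starts. To do this under the blind:
- The pharmacy randomises the first two participants as a pair in opposite orders.
- They start in turn, and the gate opens after both complete five days.
- If one withdraws before five days, the pharmacy gives the replacement, already provided for in Section 11.3, the same order before the gate opens. A kansui-first withdrawal is then always replaced kansui-first, and the replacement does not show which member was on kansui.

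Having the pharmacy or SMC simply confirm a completed kansui course would be lighter, but a delay after the first participant would tell the team that the participant was on placebo.

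*Cost.* Two sentinels in turn take 2 × 5 = 10 days instead of 5, so about five more days, or about a week if releases keep to the protocol's weekly rhythm. Each pair member replaced adds about five days. No participants are needed beyond those replacements. The team knows that the first two have opposite orders, so unblinding one, or guessing correctly from bowel effects, reveals the other: two of the six in the cohort.

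**Virologic rule.** Reword the synopsis to match Section 10.4: two consecutive values above 200 copies/mL, or one above 1000. This is a wording correction only.

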PLANNED INTERIM ANALYSES	During the study, safety will be monitored by a Safety Monitoring Committee (SMC), which will be led by an HIV specialist. The SMC will review all study procedures before the initiation of the study. They will have the full and final authority to stop the study for any safety concern at any point. Given the unknown safety profile of Euphorbia kansui , the first participant in each dosing level will complete 5 days of study prior to any further participants commencing the study. The decision to proceed with further drug administration will be taken by the Principal Investigators, taking into consideration clinical and laboratory adverse events. The decision to proceed with the next dosing level will be taken by the SMC. Specifically, dosing will be stopped and the SMC will be notified if one Grade 4 or two Grade 3 drug related adverse events or laboratory abnormalities are reported, if a participant develops virologic failure (defined as any HIV-1 RNA levels >200 copies/mL or a single HIV-1 RNA level >1000 copies/mL), becomes pregnant or initiates breastfeeding, or is required to initiate one of the prohibited concomitant medications listed in section 7.1. If stopping/pausing criteria are not met, the remainder of the dosing cohort will be enrolled/dosed the subsequent week. The study will proceed to the next dosing level provided the

	stopping/pausing criteria are not met. A University of Utah Department of Medicine faculty member who is not otherwise involved in the study and who will not communicate with the study investigators regarding any aspect of the SMC reports will prepare the monitoring reports. The SMC will review accrual, adverse events summaries, CD4+ T-cell counts and HIV RNA levels/suppression over time, off-study rates and completeness of follow-up, by dose cohort.

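### One possibly related Grade 3 event holds enrollment under Section 13, but under Section 10.4 and the synopsis it falls below the graded trigger and the cohort goes on

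*Combined protocol and SAP*

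**What the plan says.** **Section 10.4.** After the first participant at a dose level has completed 5 days, "The decision to proceed with further drug administration will be taken by the Principal Investigator", who weighs clinical and laboratory adverse events. The graded trigger reads "dosing will be paused and the SMC will be consulted if one Grade 4 or two Grade 3 drug related adverse events"; abnormal laboratory results of those grades count as well. Items 1a and 1b of the numbered list repeat these counts. The section then sets the default: "If stopping/pausing criteria are not met, the remainder of the dosing cohort will be enrolled/dosed the subsequent week". Moving to the next dose level is an SMC decision.

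**Synopsis, Planned Interim Analyses.** The counts and the default sentence are the same, but the action is worded differently: "dosing will be stopped and the SMC will be notified if one Grade 4 or two Grade 3 drug related adverse events"; here too, abnormal laboratory results count.

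**Section 13.** The rule here is "Grade 3 AEs thought to be possibly caused by the intervention and any Grade 4 AEs will result in a hold" on future enrollments "until a decision to proceed or to stop the study is made by the SMC". The contrasting sentence just before it is "If there is evidence for a Grade 3 AE that is not caused by the study drug, the study will continue as planned". On scheduled meetings, "The SMC will meet after completion of each dose cohort to review safety data", no earlier than two weeks after the last dose.

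**The concern.** The three places should describe one safety rule. For a single Grade 3 event that may be drug-related, they do not. Section 13 stops enrollment and reserves the decision to the SMC. Section 10.4 and the synopsis treat the graded criteria as not met and leave continuation to the investigator.

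Safety is the primary objective, and Section 10.4 gives the unknown safety profile as the reason for observing the first participant before others start. The same section names diarrhea as the most likely expected event and grades seven or more extra stools a day as Grade 3. One related Grade 3 event is therefore a case the plan should settle in advance.

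The choice of decision-maker matters most in cohort 2. Section 8.2 keeps the investigator and study team blind to treatment order, while Section 13 gives the SMC access to treatment assignment. The SMC is better placed to judge whether a lone Grade 3 event points to kansui. Its scheduled safety meetings, however, come only after a cohort is complete. Unless the Section 13 hold is applied, none of them falls before the rest of that cohort is dosed.

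**Working it through.** The plan states no operating characteristics for these rules and no adverse-event rates, so there is no figure to reproduce and I attach no probability. The check compares the texts case by case, then counts participants from the design.

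**1. Instruction by case**

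| Event | Section 13 | Section 10.4 | Synopsis |
|---|---|---|---|
| One Grade 3, not caused by drug | Continue | Graded trigger not met | Graded trigger not met |
| One Grade 3, possibly related | Hold enrollment; SMC decides | Graded trigger not met; rest of cohort proceeds next week if the investigator agrees | As 10.4 |
| Two Grade 3, drug-related | Hold enrollment; SMC decides | Pause dosing; consult SMC | Stop dosing; notify SMC |
| One Grade 4, drug-related | Hold enrollment; SMC decides | Pause dosing; consult SMC | Stop dosing; notify SMC |
| One Grade 4, judged unrelated | Hold enrollment; SMC decides | Graded trigger not met; criterion 5 applies if believed life-threatening | Graded trigger not met; criterion 5 not listed |

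The rules part in the second and fifth rows.

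**2. Is the Section 13 trigger a single event?** Its operative sentence is plural but states no number. The sentence before it concerns one Grade 3 event and turns on cause, not count. A single possibly related event is the natural reading, though it is an inference.

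**3. What counts as drug-related?** Table 2 in Section 10.1 has four categories: definitely, probably, possibly and unrelated. The only cut-off in Section 10.4 is in the lead-in to criterion 1, which is at least possibly related. I apply that cut-off throughout. A stricter meaning would widen the gap with Section 13.

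**4. How large is the Grade 4 gap?** Table 1 describes Grade 4 as life-threatening. Criterion 5 in Section 10.4 covers clinical reasons the physician believes life-threatening and has no relatedness condition. It should catch most clinical Grade 4 events, which leaves mainly Grade 4 laboratory values judged unrelated. The synopsis omits criterion 5.

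**5. How many participants depend on the answer?** The inputs are the cohort sizes in Section 14.5 (2 and 6) and the rule that the first participant at each level goes alone.

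- Cohort 1: 2 − 1 = 1 participant not yet started.
- Cohort 2: 6 − 1 = 5 participants not yet started.

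These are maxima for one event in a first participant. The number falls with each later start. It reaches 0 at the last participant of a cohort, since escalation goes to the SMC anyway. It may also be smaller if some participants are already enrolled but not dosed, because Section 13 speaks of enrollment only.

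**The case against.** The best defense is that the texts govern different actions: Section 13 holds enrollment and Section 10.4 pauses dosing. A site could obey both by holding enrollment at one Grade 3 event and pausing all dosing at two. The default sentence applies only when stopping or pausing criteria are not met, and a Section 13 hold could be read as one of those criteria. This reading is available, but the document states it nowhere. It also fits poorly with a default that expressly covers enrollment as well as dosing and follows directly on the Section 10.4 criteria.

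The safeguards are real. Section 10.4 also acts on virologic failure, pregnancy or breastfeeding, prohibited medication and criterion 5. Sections 10.3 and 13 provide 48-hour reporting, weekly team review for the first 2 months, and email contact for Grade 3 or 4 events. Section 10.3 adds reporting to the SMC, and the SMC may stop the study at any time. Section 13 expects gastrointestinal symptoms to be mild. All of this stands and limits the consequence, but none of it says which rule prevails.

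A reader might infer more in four ways that the documents do not support:

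- **That below two Grade 3 events the cohort continues automatically.** It does not. The investigator must decide, taking adverse events into account.
- **That unrelated Grade 4 events generally escape Section 10.4.** Criterion 5 reaches most clinical ones.
- **That 6 of 8 participants are exposed to the conflict.** Adding 1 and 5 needs a separate event in the first participant of each cohort.
- **That criterion 1, whose lead-in refers to serious events, excludes non-serious Grade 3 events or adds a separate rule for serious events of lower grade.** Items 1a and 1b most naturally repeat the thresholds in the narrative text, so no new serious-event criterion follows.

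**Conclusion.** The inconsistency is real and sits in current text. For one Grade 3 event at least possibly related to study drug, Section 13 holds enrollment for the SMC. Section 10.4 and the synopsis let the rest of the cohort proceed on the investigator's decision. Nothing ranks the two rules or presents them as tiers. One such event in a first participant affects at most 1 remaining participant in cohort 1 or 5 in cohort 2. The gap for unrelated Grade 4 events is smaller and mainly concerns laboratory values.

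The conclusion rests on reading the Section 13 trigger as a single event and on drug-related including possibly related. The documents do not show which rule the sponsor intended. Preferring the stricter one is a judgment, based on its being already written into Section 13 and on the plan's stated caution about an unknown safety profile. The loss of protection is limited, but the point should be fixed because the correction costs little.

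**What to change.** State one two-step rule in identical words in the synopsis, Section 10.4 and Section 13:

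1. One Grade 3 adverse event at least possibly related to study drug, or any Grade 4 adverse event, holds further enrollment, and also first dosing of participants not yet started, until the SMC decides.
2. One Grade 4 or two Grade 3 drug-related adverse events or laboratory abnormalities, whether or not serious, pause all dosing pending SMC review. Define drug-related as possibly, probably or definitely related under Table 2.

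Use the same verbs throughout; at present the synopsis has dosing stopped and the SMC notified, while Section 10.4 has dosing paused and the SMC consulted. Amend the default sentence in the synopsis and Section 10.4 so that the cohort continues only if neither step is triggered. No new serious-event criterion is needed, and no exceptions to the Grade 1 or 2 statements.

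This is a wording amendment with no extra visits or data. Its downside is a possible short enrollment delay while the SMC reviews a single Grade 3 event.
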